2.2 Aims

Healthcare technology assessment is the multidisciplinary evaluation of medical technologies with regard to **feasibility, safety, efficacy**, indications for use, cost, and cost-effectiveness. A complete assessment should explore the scientific, ethical, economic, and social reasons for adopting a technology and it may influence the quality of service and distribution of resources.

In this multicenter study, we aim to assess the first 3 important criteria.

Aim 1 – To determine the **feasibility** of using a wireless system immediately after delivery and for the first 2h of age, while in the obstetrical center under unsupervised parents' care. The following outcomes will be measured for both wired and wireless systems:

- a. Percentage of time for which HR, RR, SpO₂ and T_{skin} data are displayed.
- b. Occurrence of gaps in signal detection/recordings (% and length).
- c. Causes of the gaps in signal detection/recordings.
- d. Descriptive analysis of user surveys and their satisfaction with the wireless system.

Aim 2 - To investigate the **safety** of using this wireless system immediately after delivery and for the first 2h of age. The following outcomes will be measured for both wired and wireless systems:

- a. Skin score to be determined by a blinded dermatologist using de-identified pictures of the skin after removal of the sensors of each system.
- b. Pain scale to assess any discomfort or pain during the removal of the sensors.
- c. Clinically significant events detected by the wired system (HR < 100 bpm or SpO₂ < 80%) but missed by the wireless system.

Aim 3 – To assess the **accuracy** of this wireless system in measuring HR, RR, SpO₂ and T_{skin} signals compared with the “standard of care” wired system. The following outcomes will be computed:

- a. Correlation coefficient
- b. Slope
- c. Variance accounted for
- d. Bias

Further subgroup analyses will be conducted to assess for systematic differences in feasibility, safety, and accuracy of the wireless system between the following:

- High vs. Low and Middle income countries
- Female vs. Male subjects
- Term vs. Preterm (born < 37 weeks gestational age) infants
- C-section vs. Vaginal delivery

- Skin pigmentation

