3.3.2.2 Eligibility Criteria

Inclusion Criteria
Infants born by vaginal or C-Section delivery at any of the participating centers, with \geq 35 weeks gestational age and judged clinically stable immediately after birth.*
Exclusion Criteria
Skin abnormality that precludes sensors placement.
Infants born at <35 weeks gestational age
Clinically unstable infants born at \geq 35 weeks **

*Clinically stable immediately after birth will be defined for the purposes of this Study as neonates not requiring neonatal resuscitation as determined by the MUHC “Neonatal Resuscitation within the Birthing Centre Working Protocol” (Appendix 3)

** Clinically unstable immediately after birth will be defined for the purposes of this study any neonate requiring interventions in accordance with MUHC MUHC “Neonatal Resuscitation within the Birthing Centre Working Protocol” (Appendix 3).

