As part of the Smart Hospital Project, this Study and potential future research studies to improve the quality, accuracy and efficiency of monitoring neonates admitted in the NICU, the participants' information may be shared with academic or commercial third parties and used by the research team in other related research studies. Any use of the RI-MUHC and participating site's data in future research studies will be approved by competent research ethics boards and no data that could identify the participant will be shared. Participants at all participating sites will be asked to consent to the sharing of their data collected during this study as well as for use in future research in the field of neonatal care and monitoring. The participants' data will be kept confidential to the extent required by applicable laws. The research agreements with the participating sites will include all the terms and conditions required for the use and sharing of the data from participating sites.

4 Statistical Analysis and Rationale

Sample size: The proposed sample size is 100 newborns/site (n=600) to be recruited over 2 years from start of the Study at each site.

The expected mean and standard deviation are required for estimating the mean effects which is used to determine the absolute precision. In our first study with wireless sensors (see preliminary data) or *phase 1a*, 100 patient recordings (25 infants x 4 days) were expected but only 96 were obtained, resulting in a 4% drop-out rate. Further, the average coverage across wired HR signals was $98.7 \pm 2.2\%$, while that of wireless signals was $85.3 \pm 14.3\%$. Assuming a two-sided significance of 0.05, a study power of 0.9, and accounting for the drop-out rate of 0.04 in all calculations, we can expect an effect size of 2.7% in HR coverage, with the selected sample size of 600 infants. In the case of SpO₂ monitoring, the average coverage was $93.9 \pm 6.3\%$ in the wired system and $66.5 \pm 20.8\%$ in the wireless. In our proposed study, we

can thus expect a difference of 3.46% in SpO₂ coverage. For the statistical measures used to assess the agreement between the wired and wireless vital signals, the average findings from *phase 1a* are reported in the Table. Using the same parameters listed previously, the margin of error expected for each statistical measure in the proposed study can be found.

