5.1 Recruitment plan and consent of participants

At each participating site, the local research team will meet with the obstetrical team to identify potential candidates for participation in the study. Following that, eligible patients will be approached early in their labor stage to assess willingness to participate. If consent is obtained, the research team members will follow the course of the delivery. At the time of birth, infants will only be included if ≥ 35 weeks of gestational age and clinically stable as determined by the attending pediatrician. Written consent will be obtained from parents prior to enrollment. The study protocol has been designed respecting the special moment around birth. Hence, parents will be approached and receive explanation about the study design before delivery and given ample time to make an informed decision. Families will be able to withdraw from the Study at any time. However, any data collected up to date of withdrawal will not be destroyed in order to maintain the integrity of the study design. No further data will be collected once a participant is withdrawn from the Study.

As the study is not a randomized clinical trial a Data Safety and Monitoring Committee (DSMC) will not be established. However, interim evaluations for safety will be done by the lead site after 200 and 400 patients have been studied to review data related to safety, including skin lesion, pain scores, and HCPs survey responses. Any adverse event or evidence of discomfort during monitoring, including placement and removal of sensors (expected to be negligible) will be recorded and reported to the local investigator and the Principal Investigator at the lead site.

Recruitment material in the form of posters and brochures will be provided to all the sites explaining the Study and how to get additional information if interested.

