1. PATIENT INFORMATION

Patient ID (code)*	Sex	Type of delivery	Gestational age (at birth)	Time of birth (HH:MM)	Birth weight (grams)	APGAR score (1, 5 and 10')	Munsell Scale Score
R-_____	 M  F	 Vaginal  C-section	____ weeks ____ days				

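### The only gestational-age analysis is a split at 37 weeks in a cohort that starts at 35 weeks; a continuous term, from data already recorded, would usually tell more

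*Combined protocol and SAP*

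**What the plan says.** Section 2.2 (Aims) introduces five subgroup comparisons: "Further subgroup analyses will be conducted to assess for systematic differences in feasibility, safety, and accuracy of the wireless system between the following". The one that concerns maturity is "Term vs. Preterm (born < 37 weeks gestational age) infants".

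Eligibility sets the lower limit of the cohort. Section 3.3.2.2 excludes "Infants born at <35 weeks gestational age", and section 5.1 repeats the limit as a check at delivery: "At the time of birth, infants will only be included if ≥ 35 weeks of gestational age and clinically stable".

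Appendix 1, part 1 (Patient Information) has a column "Gestational age (at birth" with separate blanks for weeks and days, so age is captured to the day.

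Section 4 gives the sample size of 600 and the planning values for the whole study. It names no subgroup model, no continuous gestational-age term, no expected number of preterm infants and no precision for this comparison.

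**The concern.** The cut and the entry limit are only two weeks apart. The preterm group is therefore a narrow band at the lower edge of the cohort, and every infant in it has been judged stable. Within each group the split treats infants as alike: 35+0 and 36+6 count the same, and so do 37+0 and 41+0.

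Two things are at stake. First, if few infants fall in the band and performance changes gradually with maturity, a two-group comparison is a weak way to detect the change, and the plan does not tell the reader how weak. Second, a result headed 'preterm' can be read more widely than the cohort allows. Section 2.3 speaks of improving monitoring for all neonates, and section 3.3.5 foresees reuse of the data in research on infants in the NICU, while this study enrols nobody below 35 weeks. The point about the label needs no numerical assumption.

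**Working it through.** **Inputs from the documents (section 4).** Sample size 600. Test settings: "Assuming a two-sided significance of 0.05, a study power of 0.9". Attrition: "accounting for the drop-out rate of 0.04 in all calculations", so 600 × 0.96 = 576. Phase 1a SDs: wireless heart-rate (HR) coverage 14.3 points, wireless SpO₂ coverage 20.8 points, HR bias 0.32 bpm, SpO₂ bias 1.4 points.

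**Assumption.** The share p born at 35+0 to 36+6 is not given. I use 5%, 10% and 20%.

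**Step 1: the plan's own figure.** The multiplier is 1.960 + 1.282 = 3.2415. Then 3.2415 × 14.3 × √(2/576) = 2.73, which matches the stated 2.7 points for HR coverage. The plan does not print its formula. The same one with 20.8 gives 3.97 rather than the stated 3.46 for SpO₂, so only the HR figure serves as a benchmark below.

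**Step 2: detectable term-preterm difference.** With n₁ = 576p and n₂ = 576 − n₁, the difference detectable with 90% power is 3.2415 × SD × √(1/n₁ + 1/n₂). The square root is 0.191, 0.139 and 0.104 for the three shares.

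| Assumed share | n₁ (per site) | HR coverage | SpO₂ coverage | HR bias | SpO₂ bias |
|---|---|---|---|---|---|
| 5% | 29 (about 5) | 8.9 points | 12.9 points | 0.20 bpm | 0.87 points |
| 10% | 58 (about 10) | 6.4 points | 9.4 points | 0.14 bpm | 0.63 points |
| 20% | 115 (about 19) | 4.8 points | 7.0 points | 0.11 bpm | 0.47 points |

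For HR coverage these are 8.86/2.73 = 3.2, 6.44/2.73 = 2.4 and 4.83/2.73 = 1.8 times the whole-study figure. That figure describes wired versus wireless, not one group of infants versus another, so the ratio is a yardstick and not a like-for-like comparison. The documents give no SDs for the skin or pain scores, so I make no corresponding calculation for safety.

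**Step 3: information on a trend kept by the split.** If the outcome is linear in gestational age, the share kept is the squared correlation between age and the indicator for <37 weeks. For a normal variable cut at its p-th quantile this is φ(z_p)² / [p(1 − p)]:

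- 5%: 0.1031² / 0.0475 = 0.224, equivalent to 576 × 0.224 = 129 infants
- 10%: 0.1755² / 0.09 = 0.342, equivalent to 197 infants
- 20%: 0.2800² / 0.16 = 0.490, equivalent to 282 infants
- 25%: 0.3178² / 0.1875 = 0.539, equivalent to 310 infants

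If a linear test had 90% power, the split would have about 33%, 47% or 62% at shares of 5%, 10% or 20%.

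**Step 4: does truncation at 35 weeks change this?** I simulated age in days, restricted to 35+0 to 41+6, with an assumed mean of 38.5 to 39.5 weeks and SD of 1.2 to 2.0 weeks. The preterm share was 2% to 20% and the split kept 12% to 50%, in line with Step 3. Age in completed weeks kept 94% to 97%, so the loss comes from the two-group cut and not from rounding.

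**The case against.** The cut is defined in the line that introduces it, and the 35-week limit is stated in several places. Sections 1.2 and 2.3 describe a low-risk population. There is no contradiction between the subgroup and the eligibility criteria, and this is one of five further subgroup analyses in a cohort study meant to inform a later trial. All of that stands.

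A slope per week also answers a somewhat different question from a group contrast, and it adds an assumption about functional form. That stands too. It is why the split should be kept as a descriptive table and not removed.

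Three stronger readings are tempting, and the documents do not support them.

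- *That most of the information on maturity is thrown away.* This needs a preterm share below about 20% and a roughly linear effect. At 25% the split keeps 54%, and with a real step at 37 weeks it loses little or nothing. The plan gives no gestational-age distribution. Nor are the data lost: weeks and days stay on the form, and nothing bars a continuous analysis.
- *That the comparison is too imprecise in general.* The arithmetic shows this for coverage only. For bias, the detectable differences of 0.11 to 0.20 bpm and 0.47 to 0.87 SpO₂ points are small.
- *That a null result will be reported as no difference.* No passage says so. The plan speaks only of looking for systematic differences, and names no subgroup test and no equivalence conclusion.

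Finally, the SD of 14.3 may not carry over. Section 1.3 says that phase 1a used ANNE One in NICU infants for 8 hours a day, and that the chest sensor was then modified in size, shape, antenna position and adhesive. It is the plan's own planning value, but the coverage figures built on it are illustrative.

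**Conclusion.** The point holds as a modest improvement to an analysis choice; it is not an error or an inconsistency. From the text alone, 'preterm' in this study can mean only stable infants of 35+0 to 36+6, and the one named analysis uses less than the form records.

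The size of the loss is conditional. Under linearity, and at an assumed share anywhere from 5% to 20%, the split keeps between about a fifth and a half of the information on a trend. For HR coverage its detectable difference is roughly two to three times the whole-study figure. A share below 20% is plausible in a low-risk cohort from 35 weeks, but it remains an assumption. The imprecision applies mainly to coverage. No primary result, enrolment rule or data item is affected.

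**What to change.** - Add gestational age in days as a continuous term to the feasibility, safety and accuracy subgroup analyses: linear, with a check for curvature. Report the change per week with a 95% CI.
- Keep the 37-week split as a descriptive table, labelled late preterm (35+0 to 36+6) versus term, with the number in each group.
- State that conclusions about gestational age apply only to infants of 35 weeks and above.

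The cost is a few lines of analysis wording; the data are already on the form. The downside is the assumption of a smooth trend, which the curvature check and the retained table, where a step at 37 weeks could show, are there to cover.

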2.3 Purpose

The main objective of the AWARD Project – Clinical Study is to evaluate the use of advanced wireless sensor technology to monitor neonates after birth in low-risk infants immediately after vaginal and c-section delivery for the first 2h of age while under parents' care in the obstetrical center.

Reliable and low-cost wireless monitoring that could be used immediately after delivery would promote widespread adoption of neonatal resuscitation recommendations in LMIC, improve detection of vital signs quickly after delivery and during early unsupervised KMC, and optimize neonatal care in the obstetrical centers or during hospital stay, to prevent cases of instabilities and catastrophic events after birth, such as SUPC and its associated high mortality.

This work will promote and improve monitoring of all neonates immediately after delivery and during unsupervised KMC in the obstetrical center while under parents' care by using a non-invasive, non-intrusive, portable, and low-cost wireless technology. Potentially leading to testing of this technology during neonatal resuscitation and preventing deaths related to instabilities and catastrophic events after birth, such as SUPC in hospitals in both HIC and LMIC. Since the technology can be implemented at a low-cost as compared to standard of care wired neonatal vital signals, it can be quickly adopted for widespread use in hospitals worldwide, in particular for improving access to neonatal vital sign monitoring technology in LMIC.

3 Study Design

3.1 Study Design

Prospective International Study involving 6 centers located in 5 different countries on 3 continents. In this cohort study, all data will be collected prospectively. The focus of this study is the use of a new wireless technology for monitoring vital signs, from birth up to 2h of age, compared to data obtained from a standard-of-care wired system (**Figure 8**).

[figure not shown]

Figure 8. Study design illustration

3.2 Rationale for Study Design

The most powerful method to assess healthcare technology is the prospective, randomized controlled trial (RCT). However, RCTs are difficult to perform and expensive. Moreover, the success of RCTs requires a fundamental transformation in how they are designed, conducted, monitored, adapted, reported, and regulated, to generate the best evidence. Recently, advances in wearable technologies, data science and machine learning have begun to transform evidence-based medicine, offering a glimpse into a future of next-generation 'deep' learning medicine, which includes wearable technologies. Hence, before a RCT can be properly designed and performed, a prospective cohort study comparing 4 vital signals obtained from each patient, using wired and wireless technologies, can provide important and necessary insight on feasibility, safety, and accuracy. This will be paramount for the optimal design of a future trial.

3.3.2 Population and Eligibility Criteria

3.3.2.1 Study Population

Infants born by vaginal or C-section delivery at any of the participating sites, with ≥ 35 weeks of gestational age and judged clinically stable immediately after birth.

The number of patients expected at each site and any potential limitation is outlined on the table below:

Sites	Total Deliveries	Expected Meet Criteria	Refusal to Consent	Research team not available	Poor quality data	Potentially included for study
Royal Victoria Hospital (Lead Site)	3,300	2,805	1,042	841	280	642
UNICAMP	2,500	2,125	1,062	637	212	214
Uberlandia	2,200	1,870	935	561	187	187

Sanatorio Trinidad Palermo Hospital (3 units)	5,200	4,420	2,210	1,326	442	442
Mbuya Nehanda Hospital, Harare, Zimbabwe	11,128	9,458	4,729	2,837	945	947
Maputo Central Hospital- Mozambique	8,812	7,490	3,745	2,247	749	749
TOTAL	33,140	28,168	13,723	8,449	2,815	2,823

Infants born at \geq 35 weeks of gestational age and judged clinically stable immediately after birth are expected to represent 85% of all deliveries. Of those, 49% are anticipated to refuse consent, 30% are anticipated to be excluded due to unavailability of the research team (night and weekend deliveries), and 10% are anticipated to be excluded due to poor quality of data recordings. This leaves 10% (n=2,823) of infants that could be eligible for the study.

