3.3.3 Study Interventions

Each newborn enrolled in the Study will be monitored simultaneously by both the standard of care (control) wired vital sign monitoring system (Infinity M540 monitor, Draeger, Germany) and the wireless monitoring system (intervention) (ANNE Arc chest sensor, SIBEL Health, Illinois, USA and Limb sensor (RAD7, Masimo) (Figure 9).

Both monitoring systems, will simultaneous record heart rate, respiratory rate, oxygen saturation, and skin temperature for the first 2h of age.

Figure 9. Monitoring systems – ECG and temperature

Figure 10. Monitoring Systems – SpO2

All materials and equipment required for the conduct of the study will be provided to the participating sites by the lead site. All research team members at all sites will be trained on the placement and removal of the wireless and wired monitoring including appropriate cleaning and disinfecting protocols. Training on the use of the BioDash system will also be provided as part of the study training at all sites.

Vital Sign Monitoring:

If a baby is born via:

1. *Vaginal Delivery:* Following normal, vaginal delivery, the wireless skin sensor monitoring system (Anne Arc & RAD7 Limb,Sibel Health Inc - Masimo) will be immediately placed on the newborn. In order to promote the standard practice of bonding between newborn and mother the standard of care wired monitoring system (Infinity Monitor, Drager) will be placed on the newborn after 10-20 min of age.
2. *C-section:* Immediately before birth, the infant will be randomized for the type of monitoring system to be applied first: a) the wireless sensors (Anne Arc & RAD7 Limb,Sibel Health Inc - Masimo) or b) standard of care wired system (Infinity Monitor, Drager). In order to promote the standard practice of bonding between newborn and mother the second monitoring system will be placed on the newborn after 10-20 min of age.

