3.3.4 Data Collection

The Study research team at each site will collect standard demographic and clinical information from mothers and newborns as described in the Data Collection Form (see Appendix 1) during the 2hrs of vital sign recording (see Figure 11 below). With a stopwatch, a designated trained research team member(s) will time the recording as the period (sec.) that elapses from the application of the leads until the first display of data on the monitors, for all the sensors of both systems. Data will be continuously recorded while the mother/caregiver provides routine care. Annotations as described in the Data Collection Form will be documented by the research team regarding movements, breast-feeding attempts, cleaning/drying, patting, etc. (see Appendix 1). The vital signs data displayed on the monitors will only be visible to designated research team member(s), and all alarms will be turned off so as not to disturb parents and newborn. Any clinically relevant changes observed in vital sign parameters will be communicated by the research team member(s) to the obstetrical/neonatal team. A clinically relevant event is defined as follows: HR < 100 bpm or SpO₂ <85% (after the first 10 minutes of life) with sinusoidal wave as detected on either monitoring system during the course of the 2hr continuous monitoring. If the neonate requires any intervention to reverse instability, such as oxygen therapy and ventilator support, data collection will end but the data collected up to that time point will be included. The participating baby will not be withdrawn from the study.

The following data will be collected:

- Skin assessment:* In order to assess the safety of the wireless skin sensors, photographs of the infant's skin will be taken before device placement and after device removal. Each participating site will send de-identified digital photos coded (with the participant's study code) to the dermatologist for blinded assessment using the skin score (Neonatal Skin Condition Score - NSCS) as described in the Data Collection Form.
 - **Neonatal Skin Condition Score (NSCS)³⁷:** Photographs of the infant's skin at the site of device placement for both the chest and limb skin sensors will be taken prior to device

placement and following device removal. These photographs will then be scored by a dermatologist using the NSCS. Scores range from 3 (intact skin condition) to 9 (very poor skin condition).

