The research team will use the data collection software system called Biosensors Data Aggregation and Synchronization (BioDASH) developed by the Smart Hospital Project team in collaboration with iKinesia Inc. (Montreal, CANADA) to stream, visualize, and log data all in real-time from the standard of care wired monitoring system and the wireless monitoring system into a single study laptop (Figure 10) . Data from all monitoring devices will be aggregated and synchronized for display and logged into files for eventual offline analysis. See Figure 10 below for the BioDASH high-level system architecture and components. The BioDASH application is designed not to interfere with the patient monitor and will not store any protected health information. The streamed data logged by the application will be stored locally on the study laptop until the end of the recording period when it will be uploaded to a secure DropBox™ professional account created for the study by the Principal Investigator as well as a hard drive which will be kept in a locked cabinet in a room to which only RI-MUHC study personnel will be granted access. The data from all sites captured by BioDash will be uploaded to the secure DropBox™ professional account created for the study as well as a hard drive which will be kept in a locked cabinet in a room to which only study personnel will be granted access. The BioDash system as well as all the required devices will be provided to all participating sites by the Principal Investigator. All participating site study personnel will receive training on proper

placement of the sensors and wires, all data capturing systems and proper study conduct by the Principal Investigator and designated lead site study personnel.

[figure not shown]

Figure 11. BioDASH system architecture and components

[figure not shown]

Figure 12. Data obtained from each monitoring system will be de-identified and on a secure local server and then to a cloud before it is downloaded onto a secure data repository at the RI-MUCH for investigators' assessment.

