5. COMMENTS LOG

Comments	0 (Baseline)	1	2	3	4	5	6	7	8
Time wired Monitor									
Time wireless Monitor									
Location of newborn (k = kangaroo care, b = in bed)									
Time (clock)									
Position of newborn (s = supine, p = prone, side line =sl)									
Time (clock)									

Muscle tone (normal = n, hypotonic = hypo, hypertonic = hyper)								
Time (clock)								
Quality of reading (N/A = no issue, A = presence of artifact, P = poor signal capture)								
Time (clock)								
Interventions performed during recording (N/intervention)								
Time (clock)								
Sensor disconnection (N/reason*)								

6. COMMENTS LOG – CODE WORDS (for redcap)

Event	Drop-Down Code	Details
Kangaroo Care = KC	KC start	Start of kangaroo care
	KC end	End of kangaroo care
Nursing Care = NC	NC check	Quick nurse check (may open incubator, no real manipulation of infant)
	NC start	Routine care, that is longer than quick check, includes diaper change, feeding, etc)
	NC end	End of routine care procedures
Parent Care = PC	PC start	Holding baby, changing diaper, umbilicus care, bath time
	PC end	End of parent care procedures
Breastfeeding = BF	BF start	Start of breastfeeding
	BF end	End of breastfeeding
Repositioning = R	R supine	Baby repositioned to supine
	R prone	Baby repositioned to prone
	R Side	Baby repositioned to side
	E end	Exam end

xEvent Other	EO [specify]	Other relevant event not accounted for by annotations list please specify
Sensors (both) = S	SR start	Sensors removed for
	SR end	Sensors placed back
Chest Sensor = C	CR start	Chest sensor removed for exam
	CR end	Exam over chest sensor placed back on
	CA	Chest sensor readjustment
Limb Sensor = L	LR start	Limb sensor removed
	LR end	Limb sensor back on
	LA	Limb sensor readjustment
	LX	Limb sensor falling off [ES1]
	LH right	Limb location change – now on right hand
	LH left	Limb location change – now on left hand
	LF right	Limb location change – now on right foot
	LF left	Limb location change – now on left foot
Drager Electrodes = E	ER start	Electrodes removed
	ER end	Electrodes back on
	EA	Electrodes readjusted/moved
Massimo Oximeter = O	OR start	Oximeter removed
	OR end	Oximeter back on
	OA	Oximeter readjusted
	OH	Oximeter moved to hand
	OF	Oximeter moved to foot
Temperature and Humidity	T() H()	Temperature and humidity recording

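### The recruitment forecast anticipates excluding infants for poor-quality recordings, but no eligibility or analysis rule covers this, and lost signal is itself the Aim 1 outcome

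*Combined protocol and SAP*

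**What the plan says.** Section 3.3.2.1 sits under the heading on population and eligibility. It forecasts recruitment by site, with losses for refusal of consent, absence of the research team and poor data. On the last it says "10% are anticipated to be excluded due to poor quality of data recordings". The table puts this loss at 2,815 infants and removes it before the final column of infants who could be included.

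Section 3.3.2.2 lists three exclusions: "Skin abnormality that precludes sensors placement", gestational age under 35 weeks, and clinical instability. None concerns recording quality.

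Section 2.2 sets the Aim 1 outcomes for both systems: the percentage of time that data are displayed, "Occurrence of gaps in signal detection/recordings (% and length"), and the causes of the gaps. Aim 2c counts clinically significant events that the wired system detected and the wireless system missed.

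The data collection form (Appendix 1, comments log) records signal quality as data: "Quality of reading (N/A = no issue, A = presence of artifact, P = poor signal capture").

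Two retention rules are stated. Under section 3.3.4, if an infant needs intervention, "data collection will end but the data collected up to that time point will be included". Under section 5.1, data gathered before a family withdraws are kept. Neither addresses signal quality.

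Section 4 defines no poor-quality recording, threshold or analysis set. Its only allowance for loss is "accounting for the drop-out rate of 0.04 in all calculations", taken from phase 1a, where 96 of 100 expected recordings were obtained.

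**The concern.** Refusal and staff absence remove infants before any signal exists. Poor recording quality cannot be judged until an infant has been consented, fitted with sensors and recorded, so an exclusion on that ground comes after the outcome has been observed. For Aim 1, a poor recording is a result. Removing it because it is poor would tend to raise coverage and shorten gaps for whichever system failed. For Aim 2c, it could remove the infants in whom the wireless system missed an event because its signal was lost.

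The plan does not say what should happen to a poor recording. Six sites and the analysts have a sentence that speaks of exclusion, a form that codes poor signal as data, and no rule in section 4 to settle which governs. The decision could then be made after the data have been seen.

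**Working it through.** **1. The forecast figure.** Section 3.3.2.1 gives 28,168 infants meeting criteria and 2,815 lost to poor data. 2,815 / 28,168 = 10.0%, so the stated 10% reproduces with infants meeting criteria as its base.

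**2. Which loss section 4 carries.** The 4% drop-out leaves 600 × 0.96 = 576 infants; a 10% loss would leave 600 × 0.90 = 540. The formula (z0.975 + z0.90) × SD × √(2/n), with z0.975 + z0.90 = 3.2415, gives:

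| Quantity | SD | n = 600 | n = 576 | n = 540 | Stated |
|---|---|---|---|---|---|
| HR coverage effect | 14.3 | 2.68 | 2.73 | 2.82 | 2.7 |
| HR variance accounted for, margin | 6.5 | 1.22 | 1.24 | 1.28 | 1.24 |
| SpO2 variance accounted for, margin | 20.8 | 3.89 | 3.97 | 4.10 | 3.97 |

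The two margins match only at 576, so section 4 uses the 4% and not the 10%. The stated SpO2 coverage difference of 3.46 does not reproduce with this formula (3.97 at 576); nothing below depends on it. The loss of precision from 576 to 540 is small: √(576/540) = 1.033, or about 3%. The issue is therefore bias and not sample size.

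**3. Possible bias, as an illustration.** Inputs are the phase 1a coverage means and SDs in section 4: wireless HR 85.3 ± 14.3, wireless SpO2 66.5 ± 20.8, wired HR 98.7 ± 2.2, wired SpO2 93.9 ± 6.3. Assume that the excluded recordings are exactly the lowest fraction p of wireless coverage.

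- Normal shape: rise in mean = SD × φ(z_p) / (1 − p). At p = 0.10 the multiplier is 0.1755 / 0.90 = 0.195. HR: 14.3 × 0.195 = 2.79. SpO2: 20.8 × 0.195 = 4.06.
- Beta shape matched to mean m and SD s (as proportions): k = m(1 − m)/s² − 1, a = mk, b = (1 − m)k. HR: a = 4.38, b = 0.75. SpO2: a = 2.76, b = 1.39. Averaging above the 10th percentile gives rises of 3.58 and 4.45.

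| Fraction dropped | Wireless HR rise | Wireless SpO2 rise |
|---|---|---|
| 10% (forecast) | 2.79 to 3.58 | 4.06 to 4.45 |
| 4% (phase 1a loss) | 1.28 to 1.75 | 1.87 to 1.99 |
| Any, if quality is unrelated to coverage | 0 | 0 |

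**4. Effect on the comparison.** The phase 1a wired-wireless gaps are 98.7 − 85.3 = 13.4 points (HR) and 93.9 − 66.5 = 27.4 points (SpO2). After the 10% exclusion, 13.4 − 3.58 = 9.8 to 13.4 − 2.79 = 10.6 points remain for HR, and 27.4 − 4.45 = 22.9 (rounded down from 22.95) to 27.4 − 4.06 = 23.3 for SpO2.

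**5. If exclusion followed wired quality instead.** The same two calculations on the wired figures give rises in wired coverage of 0.4 to 0.6 points (HR) and 1.2 to 1.6 points (SpO2). This would widen the gap and not narrow it.

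**The case against.** The strongest reply is that section 3.3.2.1 is capacity planning. It introduces expected numbers and potential limitations, speaks of what is anticipated, and ends with infants who could be eligible. Section 3.3.2.2 governs eligibility and has no quality criterion, and nobody is told to drop an infant. This stands: a reader might infer that the protocol prescribes the exclusion, and it does not. The harm is conditional on the forecast being acted on.

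Other text favours retention, which also stands. Aim 1 makes gaps an outcome, the form codes poor signal as data, and two rules keep partial data. A reader might infer that everything said about poor recordings points to exclusion, or that section 3.3.4 holds the only rule for incomplete recordings. Neither is so, given Aim 1, the form and section 5.1. But none of this text settles whether a recording of poor quality stays in the analysis.

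Three further inferences are not supported.

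- A reader might call the base of the 10% unclear, since 2,815 is 46.9% of the 28,168 − 13,723 − 8,449 = 5,996 infants left after the other losses. The text ties all three percentages to infants meeting criteria, and the arithmetic agrees. So high an implied rate among recorded infants suggests rough planning figures.
- Because "the second monitoring system will be placed on the newborn after 10-20 min of age", a reader might expect coverage to be distorted by a fixed 120-minute denominator. No section proposes one.
- The table's rows sum to 642 + 214 + 187 + 442 + 947 + 749 = 3,181, against a printed total of 2,823. This is clerical. The smallest site forecast, 187, still exceeds the 100 needed.

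Finally, the illustrated rises come from 8-hour neonatal intensive care recordings with an earlier sensor, and assume that exclusion falls exactly on the worst wireless recordings. Poor quality could also arise in the wired system or the logging software. The rises are therefore the top of a conditional range.

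**Conclusion.** The concern holds in a limited form. The plan forecasts a post-recording exclusion that its eligibility list omits, its analysis section does not handle, and its first aim contradicts. If applied, it selects infants on the Aim 1 outcome and could remove missed events from Aim 2c.

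The size cannot be known from the documents. Under the phase 1a illustration, mean wireless coverage would rise by at most about 2.8 to 3.6 points for heart rate and 4.1 to 4.5 for SpO2, and by nothing if quality is unrelated to wireless coverage. Wired coverage would rise instead if exclusion followed wired quality.

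A reader might infer that the exclusion could reverse the comparison. On the phase 1a figures it would not: about 10 and 23 points would still separate the systems. What is at risk is the reported level of coverage and the count of missed events. This is worth correcting before analysis because the correction is simple.

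**What to change.** - **Section 3.3.2.1:** delete the poor-quality loss or reword it so that it cannot be read as an analysis exclusion. Correct the table total at the same time.
- **Section 4, Aims 1 and 2:** state that every infant with a sensor placed stays in these analyses whatever the recording quality, with coverage scored as observed for each system.
- **Section 4, Aim 3:** limit any signal-quality filter to the sample pairs used for agreement. Pre-specify it, apply it identically to both systems, and report the fraction removed by system and site.

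The cost is protocol and analysis wording, plus reporting of the fractions removed. No extra infants are needed. The downside is that reported coverage may be slightly less favourable.
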